APPENDIX G – MANIFEST REFRACTION

Manifest refraction will be performed using the CTS. For more detailed instructions refer to the CTS manual.

Beginning Approximate Refraction

The beginning approximate refraction will be plano for all eyes to facilitate masking.

INITIAL MANIFEST REFRACTION

1. Determine spherical lens power

The phoropter is placed and centered in front of the subject's pupils for each eye. The uncorrected visual acuity of each eye is assessed and noted. Subject should be instructed to look at the smallest line that is read well. Plus power lenses should be added until the visual acuity is reduced to 20/40 or 20/50. Then reduce the power by 0.25 D at a time until the subject can read the 20/20 or 20/16 line clearly. This assumes a spherical refractive error; if the subject has some astigmatism the best visual acuity may not be 20/20. This method leads to the best sphere refraction.

2. Refine cylindrical lens axis

The Jackson Cross Cylinder (JCC) lens is used to determine astigmatism. Start with the best spherical refraction in place and any cylindrical correction that is determined from the current prescription or keratometry.

NOTE: If the initial approximate refraction is spherical (no cylindrical power), probe for cylinder by placing 0.25 D of cylinder power in the phoropter and checking the power at 45, 90, 135 and 180 degrees. If cylinder is accepted at any of these meridians, use this meridian as a starting point for the axis check. If cylinder power is rejected at all four principal meridians, the JCC is removed and the manifest refraction is purely spherical.

Refine cylindrical axis then the power, then refine the axis again.

A target of an isolated rounded letter on the 20/30 line (or one line worse than the best acuity) is used. The cross cylinder is placed with the lens rotated so that the red and white markings are 45 degrees from the power meridian in the phoropter. The lens is flipped to present two views of the letter. Instruct the subject that both views may be blurred but they are to choose the better of the two or respond that the choices look the same. The lens should be flipped quickly and the subject should give their first impression rather than studying the two images.

If the phoropter is a plus cylinder phoropter, the cylinder axis is rotated toward the white dot when the cross cylinder is in the position of the clearest images (rotate toward the red dot when using a minus cylinder phoropter). This procedure is repeated until the subject reports no difference between the two choices.

3. Refine cylindrical lens power

To check the power of cylinder, the cross cylinder should then be rotated 45 degrees so that the colored dots line up with the axis in the phoropter. Repeat the same instructions; the subject reports which option is clearer or if the options look about the same. Again, flip the cross cylinder lens between two choices. For a minus-cylinder phoropter, if the clearer image is seen when the white dot is aligned with the cylinder axis, remove 0.25 D of cylinder power. If the clearer image occurs when the red dot is aligned with the cylinder axis, add 0.25 D of cylinder power. The endpoint is the least cylinder power that makes both images closest to being equal. During the power refinement process, maintain the spherical equivalent by adjusting the spherical power by +0.25 D for every 0.50 D of cylinder increase (and vice versa).

4. Refine final spherical power

Perform a final spherical power check by asking the subject to view the 20/20 line (or larger if 20/20 is not easily read). Add or remove spherical power in 0.25 diopter steps until the maximum plus sphere that provides the subject's best visual acuity achieved.

MANIFEST REFRACTION DETERMINATION WITH DUOCHROME TESTING

The manifest refraction is determined monocularly using the duochrome technique:

- 1. Complete the initial manifest refraction and dim the room illumination completely.
- 2. Select the projector's Red/Green filter with the appropriate target. The subject is asked to fixate on letters one line above their BCDVA, but no smaller than 20/25.
- 3. Have the subject compare the letters in the red/green sides and state which letters appear sharper, clearer or better focused **or** if both sides appear equally clear. (**DO NOT** ask if the letters are "better", "darker" or "brighter")
- 4. RED IS CLEARER: Place an additional 0.25 D of MINUS spherical power. Continue adding MINUS until subject reports equal clarity between sides or until the "green" side appears clearer and in better focus.
- 5. GREEN IS CLEARER: Place an additional 0.25 D of PLUS spherical power. Continue adding PLUS until subject reports equal clarity between sides or until the "red" side appears clearer and in better focus.
- 6. MANIFEST REFRACTION: The lens with which the letters on both red and green sides appear equally clear.
- 7. Remove the Red/Green filter and recheck BCDVA.

Example:

- Manifest refraction is -1.50 +0.75 x 180
- RED is CLEARER
- ADD MINUS lens in 0.25 D steps over the manifest refraction until subject reports "EQUALLY CLEAR" or "RED CLEAR"

- -2.25 +0.75 x 180 subject reports "RED CLEAR"
- -2.00 +0.75 x 180 subject reports "EQUALLY CLEAR"
- The manifest refraction is -2.00 +0.75 x 180.

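### Appendix G's rule for holding the spherical equivalent works in minus cylinder only, yet it is stated without limit and plus-cylinder phoropters are allowed

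*Combined protocol and SAP*

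**What the plan says.** All references are to the protocol, Appendix G, unless noted.

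- **Start.** "The beginning approximate refraction will be plano for all eyes to facilitate masking". Step 2 then works from the best sphere, plus any cylinder known from the current prescription or keratometry. If there is none, it probes with 0.25 D of cylinder at four meridians. The order is axis, then power, then axis again.
- **Step 2, axis.** Directions are given for both instruments. The plus-cylinder one reads: "If the phoropter is a plus cylinder phoropter, the cylinder axis is rotated toward the white dot"; the opposite direction for minus cylinder follows in brackets.
- **Step 3, power.** The dot instruction opens with one type only: "For a minus-cylinder phoropter, if the clearer image is seen when the white dot is aligned with the cylinder axis, remove 0.25 D of cylinder". The red-dot counterpart and a sentence on the endpoint follow. The compensation rule comes last, introduced as applying throughout power refinement: "maintain the spherical equivalent by adjusting the spherical power by +0.25 D for every 0.50 D of cylinder increase (and vice versa").
- **Step 4, sphere.** "Add or remove spherical power in 0.25 diopter steps until the maximum plus sphere that provides the subject's best visual acuity achieved".
- **Duochrome.** The recorded manifest refraction is "The lens with which the letters on both red and green sides appear equally clear".
- **Worked example.** It is written in plus-cylinder form: "Manifest refraction is -1.50 +0.75 x 180".

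No plus-cylinder instruction for cylinder power or for the accompanying sphere change appears anywhere in the documents. Appendix G refers to the CTS manual for more detail.

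**The concern.** The compensation rule carries a sign, and the right sign depends on the instrument. The text gives one sign and no restriction, in an appendix that expressly provides for both instruments. A plus-cylinder site that follows it literally moves the spherical equivalent while being told to hold it still.

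The cross-cylinder comparison relies on the circle of least confusion lying near the retina, which is the reason for holding the spherical equivalent during refinement. A plus shift fogs the eye, so the cylinder power endpoint becomes less reliable, as does the axis check repeated after it. Nothing later in Appendix G returns to cylinder power or axis.

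The manifest refraction feeds:

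- monocular DCIVA (Section 18.2.1, endpoint 4) and BCDVA (Section 18.3.1, endpoint 1), through Table 7 in Section 9.7;
- the defocus curve (Appendix H; Section 18.2.1, endpoint 5);
- contrast sensitivity (Section 18.3.2), where Appendix I itself stresses proper astigmatic correction;
- Section 18.2.4, item 3c, which repeats the astigmatism analysis with eyes grouped on postoperative refractive cylinder. The cut there is 1.0 D, so an error in cylinder could move an eye between groups.

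Co-primary effectiveness endpoints 1 to 3 are uncorrected acuities and do not use the manifest refraction.

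**Working it through.** **Inputs.** From Appendix G: sphere +0.25 D per 0.50 D increase in cylinder (step 3); sphere moved in 0.25 D steps (steps 1 and 4); both phoropter types allowed (step 2).

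**Formula.** Spherical equivalent SE = S + C/2, so change in SE = change in S + (change in C)/2.

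**The plan's own figure.** In minus cylinder, a 0.50 D increase means a change in C of -0.50 D:

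+0.25 + (-0.50)/2 = 0.00 D. The stated aim is met.

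**The same rule in plus cylinder.** The change in C is +0.50 D:

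+0.25 + (+0.50)/2 = +0.50 D. Leaving the sphere alone would give +0.25 D, so the rule doubles the drift it is meant to remove.

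**Sphere sign reversed in plus cylinder.**

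-0.25 + (+0.50)/2 = 0.00 D.

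**Size by amount of plus cylinder built up from zero.** The sphere moves once for each completed 0.50 D of cylinder.

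| Cylinder added (D) | From cylinder, C/2 (D) | Sphere under the rule (D) | Net shift in SE (D) | Shift with no sphere change (D) |
|---|---|---|---|---|
| 0.25 | +0.125 | 0 (not triggered) | +0.125 | +0.125 |
| 0.50 | +0.25 | +0.25 | +0.50 | +0.25 |
| 0.75 | +0.375 | +0.25 | +0.625 | +0.375 |
| 1.00 | +0.50 | +0.50 | +1.00 | +0.50 |
| 1.50 | +0.75 | +0.75 | +1.50 | +0.75 |

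An eye that accepts only the 0.25 D probe never triggers the rule. If refinement starts from a cylinder taken from keratometry or a prescription, only the later change counts. Going from +0.50 D to +1.00 D, for example, shifts SE by +0.25 + 0.50/2 = +0.50 D, not +1.00 D.

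**What survives to the recorded refraction.** Step 4 and the duochrome test both change sphere. In the worked example the refraction goes from -1.50 +0.75 x 180 (SE = -1.50 + 0.375 = -1.125 D) to -2.00 +0.75 x 180 (SE = -2.00 + 0.375 = -1.625 D). The sphere changes; the cylinder and axis do not. So the sphere is reset, and the cylinder found in steps 2 and 3 is carried through unchanged.

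**The case against.** The strongest reply is about scope. Step 3 opens its dot instructions with minus cylinder, and the red-dot sentence plainly continues under that limit without repeating it. The compensation rule could do the same. On that reading it is correct, and the fault is only a missing plus-cylinder counterpart. The sentence also states its purpose, so an experienced refractionist may use the right sign by habit. The CTS manual may cover the point, but it cannot be checked here.

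The narrow reading is possible but does not rescue the text. A sentence on the endpoint, valid for both instruments, stands between the dot instructions and the rule, and the rule is introduced for the whole of power refinement. Its closing reference to the reverse case most naturally means a decrease in cylinder. On either reading, plus-cylinder sites are left without a power or sphere instruction, and the same edit is needed.

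Two other objections stand in full. The drift is transient, because the sphere is set again twice. Exposure is also unknown: the documents do not say how many sites, if any, use plus-cylinder phoropters, and the worked example shows plus-cylinder notation without applying the rule.

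A reader might go further and infer that residual cylinder error favours the IC-8, because the lens is hypothesised to tolerate astigmatism and the monofocal fellow eye would lose more acuity. The documents do not support that. Toric lenses and limbal relaxing incisions are available only to monofocal eyes (Sections 9.6.1 and 9.6.3). IC-8 eyes may therefore carry more cylinder and meet more of the fog, which works the other way. The net direction cannot be determined.

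**Conclusion.** The defect is real and minor. As written, the rule meets its stated aim on one permitted instrument and does the opposite on the other, by +0.50 D for each full 0.50 D of cylinder added. This assumes that a plus-cylinder site applies the sentence literally, in whole 0.25 D sphere steps, and the totals in the table also assume cylinder built up from zero.

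The remaining exposure is possible error in the cylinder power and in the repeated axis check, made under fog and not re-checked. Its size is not estimated, because the documents give neither the share of plus-cylinder sites nor any figure linking such an error to acuity.

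Two stronger readings should be set aside. A reader might take the shifts as errors in the recorded spherical equivalent; step 4 and the duochrome test mean that it need not carry them. A reader might also conclude that every eye accepting cylinder at such a site is affected; the rule acts only once cylinder has changed by 0.50 D. No bias toward either lens is claimed.

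**What to change.** In step 3, state the sphere adjustment by instrument: for each 0.50 D increase in cylinder power, change the sphere by +0.25 D on a minus-cylinder phoropter and by -0.25 D on a plus-cylinder phoropter, and do the reverse for a decrease. Beside the existing minus-cylinder instruction, add its plus-cylinder counterpart for what the white and red dots mean for cylinder power.

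The cost is two sentences in Appendix G and a note in examiner training. No testing is added, and no analysis or sample size changes.

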APPENDIX H – DEFOCUS CURVE TESTING

Defocus curve testing will be done using the CTS computerized testing system. For detailed instructions refer to CTS user manual. The laptop will show the test, distance, light level and the correction needed for the testing.

Defocus curves will be performed monocularly and binocularly using ETDRS charts in the CTS calibrated for 4-meter test distance in standard photopic conditions, with the best-corrected distance manifest refraction.

A defocus curve should be obtained by using the manifest refraction and measuring the visual acuity between +2.00 D and -5.00 D in 0.5 D defocus steps, except in the region from +0.50 D through -0.50 D, which should be done in 0.25 D steps. The examiner will progressively change the defocus in 0.50 D steps from +2.00 D to +0.50 D, then in 0.25 D steps from +0.50 D to -0.50 D, then in 0.50 D steps from -0.50 D to -5.00 D, while measuring visual acuity at each successive defocus step. No infinity adjustment to refraction is needed for defocus curve testing. Letters will be randomly presented to avoid memorization by CTS automatically.

The test heading on the laptop and the tablet will indicate which lens to use. With the lens in place the tester will begin the vision testing. The tablet will display all lines from 20/200 to 20/10.

General Instructions:

- The examiner should take precautions to remind the subject not to squint at any time during vision testing.
- Each presentation is automatically randomized to eliminate the memorization effect.
- The subject responds with the smallest line where all five letters can be correctly identified and the technician enters the line number and presses "Submit"
- The chart then randomizes, setting the selected line to the top line and a pointer is shown at the next smaller line
- The subject is then asked to read this line and the number of correct letters is entered; the pointer moves to the next line
- The test continues until the subject is no longer able to correctly identify any letters within a line
- When the test is complete the results are reported in the standard ETDRS Letter Score, Visual Acuity equivalent and logMAR equivalent

For more detailed instructions refer to the CTS manual.

APPENDIX I – CONTRAST SENSITIVITY TESTING

Contrast sensitivity testing will be done using the CTS computerized testing system. For detailed instructions refer to CTS user manual. Both photopic and mesopic with and without glare conditions will be tested. The photopic spatial frequencies tested will be 3 cycles/degree to 18 cycles/degree and mesopic spatial frequencies tested will be 1.5 cycles/degree to 12 cycles/degree.

The system will present a series of targets that determine the CSF for each spatial frequency. A white dot will appear on the laptop screen when a target is presented. Four demonstration targets will be shown alternately. Instruct the subject to answer which direction the target is pointing (a laminated card is included to hand the subject to aid in their recognition). The testing will begin with the highest spatial frequency, which will be is 18 cpd for photopic and 12 cpd for mesopic testing. The test will finish with the lowest spatial frequency, which is 3 cpd for photopic and 1.5 cpd for mesopic testing. Glare will activate and CSF will be measured for same spatial frequencies.

General Instructions

- The testing distance per M&S CTS instruction is at 8 feet for contrast sensitivity.
- Subjects should wear their best spherocylindrical refractive correction for the testing. *NOTE: Proper correction of astigmatism is particularly important for the CTS linear grating test, so that all grating orientations will be equally visible.*
- Infinity adjustment to refraction is not needed for linear contrast sensitivity testing.
- The most efficient testing order timewise is: 10 min. dark adaptation, mesopic without glare, mesopic with glare, photopic without glare, photopic with glare. This testing paradigm has been pre-programmed in the CTS.
- Daily luminance calibration must be performed to verify that the preset glare levels slightly raise normal thresholds under study conditions. This testing is "fixed" and pre-programmed in the CTS as part of the daily luminance calibration detailed in the CTS user manual. If the glare levels cause either no threshold elevation or too much threshold elevation (indicated by the results of the calibration testing) contact M&S[®] Technologies for assistance.
- Daily luminance calibration must be performed, and environmental luminance verified by the CTS photometer to ensure there are no light sources or reflecting surfaces that have higher luminance than the test chart from the subject's vantage point. Ambient luminance should be tested in a dim exam room with no light sources positioned between the subject and CTS or behind the CTS. If a higher luminance is recorded during calibration, as indicated by the CTS, lighting should be adjusted and testing repeated until luminance is within the accepted range.

APPENDIX J- DATA ENTRY AND CORRECTION INSTRUCTIONS

Electronic Case Report Forms will be completed using the Medidata RaveX system. Medidata RaveX is an electronic clinical data management system designed to streamline data collection, database entry, data queries and resolution of data clarifications. Medidata RaveX allows for sites to electronically input data from source documents and questionnaires. Every means will be taken to maintain patient confidentiality throughout data transmission and database entry.

For data collection, all data fields on the paper source documents and other required testing printouts should be entered into the electronic database eCRFs for the study in Medidata RaveX system. Each site will only have access to general information for the study and the data for their own site. All personnel, at investigational sites and AcuFocus, performing data entry or data review must perform the required Medidata RaveX training module(s) and obtain user credentials prior to performing these activities. Individual credentials must not be shared with other users and must be stored in a secure location. A copy of the training certificate must be filed in appropriate study files for each user.

RaveX EDC will accept automatically transmitted data via internet from the M&S CTS system for all vision and contrast sensitivity tests conducted with the CTS, including all visual acuities, contrast sensitivity and defocus curve data. Manifest refraction will be performed using the CTS but will be manually recorded in the source documents by the masked examiner and then entered into the EDC. In the unlikely event that the automatic data transmission mechanism in the CTS is non-functioning, the site should first check if the internet connection is available and functioning and should re-attempt to transmit the data once proper internet connection is restored. If the issue persists, the site should contact M&S immediately to resolve the issue. If M&S cannot resolve the issue in a timely manner, the site should notify AcuFocus and use source documents for visual acuities and defocus curve data as an alternative method of data collection.

Following study visits, investigative sites should complete data entry within one week (five working days) of the study visit. For data verification, correction or clarification, a Clinical Research Associate (CRA) will review the data to ensure all data are complete and logical. The CRA will then query any data field that requires clarification or correction through Medidata RaveX for resolution.

Open data queries should be resolved by the site within 10 business days. All necessary corrections are to be made directly on the original source documents and entered on to the eCRF in the Medidata RaveX study database. All data changes and reasons for change are logged in Medidata RaveX.
